contact if they do not wish to be contacted further. Starting about one week after mailing recruitment letters, a member of the study staff will call patients to ascertain eligibility and obtain informed consent from the Veteran participant and Care Partner. During the phone screen process, study staff may use their discretion with the input of the Care partners to further determine whether the patient’s decision-making capacity is intact. For the Care Partner, the Six Item Screener (SIS), a cognitive assessment instrument, will be administered by trained study staff prior to Care Partner consent. If there is any question as to whether or not a potential adult subject has decision-making capacity, study staff will consult with a qualified practitioner (i.e., the study physician or study RN) about the individual’s decision-making capacity before proceeding with the informed consent process. Because the screening and enrollment is entirely telephone based, we will seek a waiver of documentation of informed consent, as approved by the Durham VAMC IRB in our ongoing studies using similar recruitment methods.

Figure 4. Study Recruitment Pool

D.3.g. Rationale for Enrollment and Screening over the Telephone. We have opted not to enroll Veterans at a primary care visit or other in-person visit for a number of reasons. First a telephone-based strategy expands the reach of the intervention by allowing enrollment from multiple community-based outpatient care clinics and not just the main hospital clinic. Most importantly this strategy mimics more closely how this intervention would be implemented if effective. We will track number of attempts to contact, and examine differences between patients who enrolled or refused and those we were unable to contact to inform future implementation efforts.

D.3.h. Randomization Procedure. Once patients and Care Partners have provided verbal consent and completed the baseline measurement battery, study staff will randomize the Veteran to Telephone-Based Care Management (Section D.4) or Video-Enhanced Care Management (Section D.5). Randomization assignments will be performed by the study statistician and the entire study randomization will be done before patient enrollment begins. We will stratify randomization based on whether or not patients are ‘experienced with relevant technology’. Participants will be considered ‘experienced with relevant technology’ if they indicate use

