D.6.a. System Usability Scale. We will use the simplified language version of the System Usability Scale (SUS; see Appendix) to measure usability of video visits via iPad. The SUS is a widely-used, simple but reliable method to evaluate the usability of new technologies.³⁰ The SUS is well-validated and consists of 10 Likert-scaled items with scores ranging from 0 to 100.³¹

D.6.b. Participant and study staff feedback. Patients and Care Partners will participate in semi-structured interviews regarding perceived benefits and challenges of the care management program. Interviewer scripts will include open-ended questions about barriers and facilitators of success in the program, including technology-related, and as well as more specific questions to elicit stakeholder perspectives on intervention content, and recommendations for improvement (see Evaluation Table; Appendix). We will also seek feedback from primary care providers and study staff.

D.6.c. Measures of intervention effectiveness. In preparation for a future RCT, we will collect outcome measures we anticipate using to test intervention effectiveness. Patient reported outcomes will be examined at baseline and the 14-week follow-up call (immediately following completion of the 12-week intervention period that begins at week 2; Figure 3). Consistent with our conceptual framework, the balance of workload demands and capacity directly affect utilization and outcomes; thus we plan to focus on hospitalizations, ED visits, and patient-reported outcomes recommended for use in patients with MCC,¹⁶ that may be responsive to the intervention.

Hospitalizations and ED visits. To calculate this outcome, we add the total number of days a patient is in the emergency department (ED), or hospital. In order to avoid double-counting events, we only count ED visits as a discrete day if the ED visit did not lead to hospital admission. We include observation stays as hospital days. Data from the outpatient and inpatient files from the CDW will be used to generate counts of days associated with emergency care (treat and release), observation stays, and inpatient care, over the 14 week observation period. ED visits will be identified through the outpatient files according to clinic stop codes (130, 131, 102130 and 102131).³² Inpatient encounters will include total days in the hospital (DISDAY minus ADMITDAY).

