PROMIS-29. The Patient-Reported Outcomes Measurement System 29-item Health Profile (PROMIS-29) has good evidence of reliability and responsiveness, and is suitable for telephone administration. PROMIS has published its results in 20000+ adults, many with MCC, and has been recommended by the Working Group on Health Outcomes for Older Persons with Multiple Chronic Conditions, an expert panel convened by the National Institute of Aging in collaboration with Agency for Healthcare Research and Quality.¹⁶ The tool has also undergone extensive valuation work enabling translating PROMIS-29 responses into quality-adjusted life-years.³³

Physical Activity Scale for the Elderly (PASE). The PASE is a self-report, 12-item scale that measures occupational, household, and leisure activity during a one-week period.³⁴ This scale was developed for use among older adults and has been validated for use via telephone.

Medical Outcomes Study: Short Form Social Support Survey Instrument. This 8-item measure reflects how often a person looks to others for companionship, assistance, or other types of support, and is well-validated.³⁵

Depression and anxiety. It is important to note that eligibility for the current study depends on the results of a cognitive screener administered on one occasion and this does not constitute a formal diagnosis of any cognitive disorder. Nevertheless, we expect that some participants will be referred for further testing and may receive a diagnosis in a clinical setting. There have been no studies reporting harm related to receiving a diagnosis of CI; however, some groups have raised concerns about this possibility. Thus we will measure symptoms of depression (Patient Health Questionnaire [PHQ]-9) and anxiety (General Anxiety Scale [GAD]-7) at baseline and the 14 week follow-up call. The PHQ-9 is a nine item depression scale that is well validated and documented in a variety of populations including a geriatric populations and primary care settings.³⁶ The GAD-7 is a 7-item anxiety scale with good reliability, as well as criterion, construct, factorial, and procedural validity.³⁷ We will utilize a safety protocol to address suicide risk identified during the administration of study measures (Appendix).

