D.7.b. Aim 2: Assess the *usability* and *perceived value* of video-enhanced care management, compared to telephone-based, among older Veterans with medical complexity and CI. We will administer the SUS at the 14-week outcome call to participants randomized to Arm 2 (video-enhanced.), care partners, and clinical staff. If any participants choose to withdraw from this Arm, we will administer this measure prior to withdrawal. We will examine overall sample mean, median, and distributions of scores according to established thresholds (e.g. >70 = excellent usability among those aged ≥65 years). Additionally, we will look at responses to individual items to see if certain items are more frequently endorsed (e.g. technical support item) to make refinements prior to a larger RCT. We will calculate means (or medians, as appropriate) and distributions of hospitalizations, ED visits, and patient-reported outcomes (PROMIS 29, PASE, MOS Social Support, PHQ-9, GAD-7) across time points, as well as changes between baseline and 14-week follow-up, as appropriate. Because of the small sample size, we will not conduct statistical testing. However, our descriptive analyses will allow us to evaluate whether there are clinically relevant differences in mean study outcomes between the two Arms (video-enhanced vs. telephone-based). Perceived value associated with each delivery method will be explored through questionnaires and in-depth interviews with study participants and study staff.

D.7.c. Sample size considerations. This is an exploratory pilot study that is not intended to test efficacy. While the sample size chosen must reflect the pragmatics of recruitment during a short enrollment period, we will have adequate sample size to provide meaningful confidence intervals for our estimates of feasibility, and comparisons between video and telephone delivery methods, and will have sufficient diversity of input on the intervention to plan refinements, if needed, prior to testing it in a larger RCT.

D.8. Dissemination and Implementation Plan

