The results of this pilot study will provide essential information about the feasibility, acceptability, usability, and perceived value of a care management program for medically complex Veterans with CI, delivered via telephone or through video visits on iPads. By using these preliminary data to refine study methods and optimize the intervention protocol prior to conducting a large RCT, we will enhance the efficiency and overall value of the subsequent trial. Specifically this pilot study addresses the important question of whether providing care management via video visits is feasible in this population, and if so, whether it offers added benefits, compared to telephone. To examine video visits, we will use the Pexip Infinity application which is currently approved and in preliminary clinical use in VHA, making rapid implementation highly feasible, if proven effective.

D.9. Project Management Plan

D.9.a. Summary of Research Team Experience. The research team is comprised of investigators from the HSR&D COIN for Health Services Research in Primary Care; the Geriatrics, Research, Education and Clinical Center (GRECC) at the Durham VA, the Duke University Center for the Study of Human Aging and Development and Alzheimer's Disease Research Center. We have assembled a multidisciplinary study team with a track record of productive collaboration, as well as relevant experience with all the methodology, data sources and analytic techniques described in the current proposal.

D.9.b. Timeline. We propose a **1 year study**. As illustrated below, we expect to begin enrollment in month 4 and complete data collection by month 10. The remainder of the study period will be dedicated to analysis of the data, dissemination of study results, and preparation of an IIR to test the intervention in an RCT.

	Month											
	1	2	3	4	5	6	7	8	9	10	11	12
Project Start Up												
Finalize IRB	X	X										
Develop study database and procedures	X	X	X	X								
Intervention Implementation												
Enroll patients				X	X	X	X					
Intervention and outcome assessments					X	X	X	X	X	X		
Data Analysis												
Planning for data analysis									X	X	X	X
Data analysis and reporting/ Prepare IIR											X	X

D.10. Data Management

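### D.7.b judges arm differences in patient-reported outcomes from unadjusted summaries, none named as the one to read; a pre-named baseline- and stratum-adjusted difference with a CI is a cheap, minor improvement

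*Combined protocol and SAP*

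**What the plan says.** D.7.b (Aim 2) opens the relevant sentence with "We will calculate means (or medians, as appropriate) and distributions of hospitalizations, ED visits, and patient-reported outcomes" and continues "across time points, as well as changes between baseline and 14-week follow-up, as appropriate". It rules out statistical testing because the sample is small, then states that "our descriptive analyses will allow us to evaluate whether there are clinically relevant differences in mean study outcomes between the two Arms". It gives a usability threshold for the SUS but no relevance threshold for PROMIS-29, PASE, MOS Social Support, PHQ-9 or GAD-7.

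The inputs for an adjusted comparison already exist. D.6.c: "Patient reported outcomes will be examined at baseline and the 14-week follow-up call". D.3.h: once the dyad has consented and "completed the baseline measurement battery, study staff will randomize the Veteran". D.3.h also says "We will stratify randomization based on whether or not patients are" experienced users of tablets or video calling. Neither the baseline score nor this stratum enters the arm comparison in D.7.b.

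D.8 says the pilot addresses whether video visits are feasible and, "if so, whether it offers added benefits, compared to telephone".

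Three places describe the statistical work differently. D.7.a plans regression analyses of enrollment and completion. D.7.c expects meaningful confidence intervals. The closing section, Data Analysis and Statistical Considerations, says that no statistical analysis will be done.

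**The concern.** The plan gives its descriptive summaries a comparative job without saying which of them does it. For means in the same completers, the 14-week arm difference minus the difference in change equals the baseline difference. Chance imbalance at baseline therefore decides how far the two summaries disagree, and at about 20 per arm such imbalance is common. If the choice is made after the data are seen, a score has two chances to look clinically relevant. Medians add a further option.

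What is at stake is how the pilot's arm comparison is read when the larger RCT is planned. The stratum matters less, since stratified randomization already limits imbalance on it.

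Separately, the closing section cannot be reconciled as worded with the regression in D.7.a or the intervals in D.7.c.

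**Working it through.** The plan states no effect size, SD, power or interval width for these outcomes, so there is no figure to reproduce.

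**Inputs from the documents.** 40 dyads randomized 1:1 (D.1), so 40/2 = 20 Veterans per arm.

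**Assumptions, not in the documents.** SD = 1 at both visits; baseline/follow-up correlation r = 0.3, 0.5, 0.7; an illustrative relevance cut of 0.5 SD; no dropout.

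**Baseline imbalance.** The SE of an arm difference is sqrt(2/20) = 0.316. P(|difference| ≥ 0.3) = 2[1 − Φ(0.3/0.316)] = 0.34, and P(|difference| ≥ 0.5) = 2[1 − Φ(0.5/0.316)] = 0.11. With 18 per arm these are 0.37 and 0.13.

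**Expected 95% CI half-widths (SD units).**
- Raw 14-week difference: t(38) × 0.316 = 2.024 × 0.316 = 0.640.
- Change: 0.640 × sqrt(2(1 − r)).
- Adjusted for baseline and stratum: t(36) × 0.316 × sqrt(1 − r²) × sqrt(1 + 1/35), with t(36) = 2.028.

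| r | raw | change | adjusted |
|---|---|---|---|
| 0.3 | 0.64 | 0.76 | 0.62 |
| 0.5 | 0.64 | 0.64 | 0.56 |
| 0.7 | 0.64 | 0.50 | 0.46 |

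Against the better unadjusted summary the gain is about 0.02, 0.08 and 0.03 SD.

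**Share of trials with |estimate| ≥ 0.5 SD and no true effect, for one score.** The raw and change differences have correlation sqrt((1 − r)/2). Their joint normal distribution gives the column for either; the adjusted column is from simulation with estimated coefficients.

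| r | raw | change | either | adjusted |
|---|---|---|---|---|
| 0.3 | 11% | 18% | 25% | 10% |
| 0.5 | 11% | 11% | 20% | 7% |
| 0.7 | 11% | 4% | 15% | 3% |

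At r = 0.5, naming either unadjusted summary alone brings 20% down to 11%; adjustment takes it to 7%.

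**Disagreement.** The two unadjusted summaries fall on different sides of the cut in 20%, 17% and 13% of null trials. Differences in opposite directions, both at least 0.3 SD, occur in about 1% or fewer.

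**Cost of adjusting.** At r = 0 the adjusted half-width is 0.650, and 0.650/0.640 = 1.016, so about 2% wider on average. Break-even is r = sqrt(1 − 1/1.016²) = 0.18. Individual trials vary: simulated at r = 0, the interval was more than 2% wider in about half of trials, and the 95th percentile was about 6 to 7% wider.

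**Across scores.** At r = 0.5, treating five scores as independent, the chance that at least one adjusted estimate crosses is 1 − (1 − 0.069)^5 = 0.30. If either unadjusted summary may be used, it is 1 − (1 − 0.198)^5 = 0.67.

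**The case against.** The strongest reply is that this is a descriptive pilot. D.7.c says it is not meant to test efficacy, D.6.c collects these outcomes to prepare for a later RCT, and Aim 2 is usability and perceived value, carried by the SUS, questionnaires and interviews. Nothing planned turns on level versus change. That stands, and it keeps the point minor. It does not remove it, because D.7.b and D.8 themselves ask the descriptives to speak to arm differences.

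Four stronger readings are tempting, and the documents do not support them.
- *The arms will be compared both ways and the better result chosen.* D.7.b does not say so. Its qualifier has an innocent reading: the same sentence covers hospital and ED use, for which D.6.c defines only a 14-week count, so change is undefined there. If summaries are shown by arm, baseline imbalance will also be visible. The figures for either summary crossing show what an open choice permits, not what is planned.
- *No arm-comparison interval is planned.* D.7.c can be read as promising intervals for feasibility only or also for video versus telephone. The closing section conflicts with either reading, but that is a wording repair and lends no weight to the case for adjustment.
- *The planned summaries ignore baseline.* Change scores use it; they are simply not covariate-adjusted.
- *A single adjusted model settles the comparison.* It gives one estimate per score, not one overall.

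It is also fair that the precision gain is modest and depends on an r that the documents do not give. The stratum term alone trims the SE by only about 1 to 7% (assumed stratum effect 0.3 to 0.8 SD).

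**Conclusion.** The point holds as a cheap improvement of minor severity. The textual gap is certain: D.7.b names no carrying summary, uses no adjustment, and judges clinical relevance without a threshold. The practical size rests on the assumed equal SDs, r and 0.5 SD cut. The more secure benefit is removing the choice between summaries; the precision gain is secondary, and there is none on average over raw means below r of about 0.2.

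The limits should be stated with the result. Half-widths near 0.5 to 0.6 SD remain too wide to exclude moderate differences. Choice among scores remains, and the roughly 30% figure for five scores assumes independence. The change does not say what difference is clinically relevant. The identity linking raw and change differences applies only to means in the same completers. The arm comparison stays exploratory after the fix.

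**What to change.** - Keep all planned descriptive summaries, with medians as supplementary description.
- For PASE, MOS Social Support, PHQ-9, GAD-7 and each PROMIS-29 domain score, fit a linear model for the 14-week score with arm, baseline score and technology-experience stratum. Domains are used because D.6.c presents the instrument as a "29-item Health Profile (PROMIS-29") and defines no single total.
- Report the arm difference with a 95% CI and no p-value, labelled estimation only. Name it in advance as the estimate to read for that score. This respects the decision not to test and matches the reference in D.7.b to mean outcomes.
- State that several scores are reported with none designated as main.
- Leave hospital and ED days descriptive.
- No special interval is needed for the skewed PHQ-9 and GAD-7. In simulations with assumed skewed scores at 20 per arm, the model's t interval covered 0.946 to 0.958, while a percentile bootstrap covered only 0.914 to 0.932.
- Amend the closing section to say that no hypothesis testing will be performed, so that it agrees with D.7.a and D.7.c.

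The cost is some wording, one simple model per score and two degrees of freedom. No new data, visits or participants are needed. If baseline and follow-up were uncorrelated, intervals would be about 2% wider on average, and about 7% wider in an unlucky trial.

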- Direct identifiers will be maintained separately from data and or specimens by using a code to “identify” subjects. In a separate database (i.e., a “linking” or “cross-walk” database) this code will be linked to identifying subject information.

The patients’ right of privacy and the confidentiality of the protected health information will be guarded through strict controls and safeguards for access of the data to members of the research team. All study data will be stored on VA servers maintained by OI&T staff to comply with VA information security requirements. This includes study tracking and Datstat Ilume survey databases on server VHADURSQLH5.v06.med.va.gov, and project shared document folder \\vhadurhsrdfile1.v06.med.va.gov\projects\SECSI (usually mapped on users’ systems as P:\SECSI). Access to database and file systems is granted to research personnel via membership in Active Directory security groups created by OI&T; limited to individuals on the IRB staff listing. Members are removed from the security group when they no longer require access to study data. Data will not be stored on desktop or laptop computer hard-drives. Only VA approved staff will have access to the data file for data analysis. The PI will have ultimate responsibility of access to the data. Furthermore, data will be kept in accordance with VA records control schedule.

- Other, specify:

7. Suspected Loss of VA Information:

Should any incident such as theft or loss of data, unauthorized access of sensitive data or non-compliance with security controls occur it will be immediately reported according to VA policy. All incidents regarding information security/privacy incidents will be reported to the ISO and PO within 1 hour of acknowledgement of issue and done so using the VHADUR Research Events Report e-mail group ([contact]).

8. Reporting of Results:

- Reporting of results, such as in scientific papers and presentations, will never identify individual subjects. Data will be presented in aggregate and individual-level data will not be published.
- Other results reporting plan, describe:

Data Analysis and Statistical Considerations

Due to the small sample size, statistical analysis will not be performed on the sample.

References

Provide references, if applicable.

N/a

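### D.7.b would judge clinically relevant arm differences from descriptive means alone, though at 20 per arm the 95% interval for a difference is about ±0.64 SD and D.7.b reports no interval

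*Combined protocol and SAP*

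**What the plan says.** D.7.b (Aim 2) plans means or medians, distributions and changes from baseline for hospitalizations, ED visits and five patient-reported measures: PROMIS-29, PASE, MOS Social Support, PHQ-9 and GAD-7. It states: "Because of the small sample size, we will not conduct statistical testing". It then says that "our descriptive analyses will allow us to evaluate whether there are clinically relevant differences in mean study outcomes between the two Arms". The only threshold in the section is a System Usability Scale (SUS) score above 70, which concerns usability of the video system.

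D.7.c describes the purpose and the precision: "This is an exploratory pilot study that is not intended to test efficacy", but also "we will have adequate sample size to provide meaningful confidence intervals for our estimates of feasibility, and comparisons between video and telephone delivery methods". No confidence level or width is given.

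D.7.a plans contingency tables and regression for enrollment and study completion. D.8 says the pilot addresses whether video visits are feasible and, if so, "whether it offers added benefits, compared to telephone". The closing section, Data Analysis and Statistical Considerations, consists of one sentence: "Due to the small sample size, statistical analysis will not be performed on the sample".

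**The concern.** Dropping the test does not remove the imprecision that was the reason for dropping it. An analyst who follows D.7.b as written would report two means per outcome and leave the reader to decide whether the gap matters clinically. At this sample size a gap can be chance alone, and a real difference can be hidden.

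The sections also do not fit together. D.7.c promises intervals for arm comparisons without saying which comparisons it means. D.7.b, where the comparison is made, does not mention them. The closing section, taken at its word, would forbid them. At stake is how the arm comparison is reported and read when the team refines the intervention for the later trial.

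**Working it through.** **Inputs.** From D.1: 40 dyads, 1:1, so 20 Veterans per arm. The plan states no dropout rate. The only follow-up figure in the document is the 96% completion in the team's ongoing emergency-department trial (B.7.a); 0.96 × 20 = 19.2, or about 19 per arm. A 20% loss (16 per arm) is an assumption, used to show sensitivity. No SDs are given, so widths are in SD units. The plan gives no alpha, power, effect size or interval width, so it has no figure to reproduce.

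**Difference in follow-up means, unadjusted.** The 95% half-width is t(0.975, 2n−2) × √(2/n):

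| n per arm | standard error (SD) | half-width (SD) |
|---|---|---|
| 20 | √(2/20) = 0.316 | 0.640 |
| 19 | √(2/19) = 0.324 | 0.658 |
| 16 | √(2/16) = 0.354 | 0.722 |

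**Using the baseline value (20 per arm; r is an assumed baseline-to-follow-up correlation).** Baseline-adjusted: t(0.975, 37) × √(1−r²) × √(2/20) = 0.555 at r = 0.5 and 0.458 at r = 0.7. Change score: 0.640 × √(2(1−r)) = 0.640 at r = 0.5 and 0.496 at r = 0.7.

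**Gaps produced by chance.** The benchmark of 0.5 SD is chosen for this review and is not in the document. With no true difference and 20 per arm, one outcome on follow-up means shows a gap at least that large with probability 2 × (1 − Φ(0.5/0.316)) = 0.114. For at least one of five measures, independence gives 1 − (1 − 0.114)⁵ ≈ 0.45. Simulation with equally correlated outcomes gives 0.453 at correlation 0, falling to 0.302 at correlation 0.7. Baseline adjustment lowers these rates:

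| Analysis | one outcome | at least one of five (correlation 0.7 to 0) |
|---|---|---|
| Follow-up means | 11% | 30-45% |
| Baseline-adjusted, r = 0.5 | 7% | 19-30% |
| Baseline-adjusted, r = 0.7 | 3% | 9-13% |

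**Real differences hidden.** With a true difference of 0.5 SD and 20 per arm, the observed difference in follow-up means falls below 0.25 SD with probability Φ(−0.25/0.316) = 0.21. The 95% CI excludes zero in 34% of trials (noncentral t).

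**Proportions.** For a rate p among all 40 enrolled, the 95% Wilson limits are 0.352-0.648 at 50%, 0.652-0.895 at 80% and 0.769-0.960 at 90%, that is about ±15, ±12 and ±10 points. Between arms, with equal rates and Wilson limits l and u per arm, the Newcombe half-width is √((p−l)² + (u−p)²). At 20 per arm and 50%, l = 0.299 and u = 0.701, giving 0.284. At 80%, 90% and 95% the results are 0.247, 0.214 and 0.191. At 16 per arm the range is 0.311 (50%) to 0.221 (95%).

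**Which comparisons D.7.c can mean.** It cannot mean a between-arm SUS comparison among Veterans, because D.7.b will "administer the SUS at the 14-week outcome call to participants randomized to Arm 2" (plus care partners and clinical staff). That leaves feasibility proportions, at about ±19 to ±28 points, or outcome means, at about ±0.64 SD unadjusted. Both are wide for an arm comparison.

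**The case against.** The strongest reply is that the plan as a whole does promise intervals. D.7.c directly follows D.7.b and names video-telephone comparisons, so an analyst would have to ignore it to report none. That stands: the defect is that D.7.b does not carry the intervals over and that no width or threshold is stated, not that intervals are absent from the plan.

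Second, the closing sentence gives the same reason as D.7.b's no-testing sentence and is probably shorthand for it. That is the likelier reading, but the sentence does not say so. Even read literally it does not clearly reach all of D.7.a's regression: a model of enrollment must include people who did not enroll, so only the completion model plainly falls under it.

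Third, this is a declared exploratory pilot. Aim 2 concerns usability and perceived value, which interviews and questionnaires also inform, and no progression rule uses arm means. This limits the consequence, but the D.7.b sentence still claims more than point differences can show. D.8's reference to added benefits can be read as perceived value, but it does not say that either.

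Fourth, the widths depend on choices. The 96% figure implies ±0.66 SD rather than ±0.72, baseline adjustment narrows further, and SD-based widths suit the scale scores better than skewed day counts. All of this is granted, and the ranges above show it.

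A reader might go further and infer that the arm differences will be used to size the later trial. The document does not say so; D.8 speaks of "using these preliminary data to refine study methods and optimize the intervention protocol prior to conducting a large RCT". A reader might also infer that 40 dyads are too few. D.7.c disclaims an efficacy test and rests the number partly on recruitment pragmatics and diversity of input, so lack of power is not the criticism.

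**Conclusion.** The point holds as one of interpretation and internal consistency, and should be fixed. Descriptive means at 20 per arm do not allow the evaluation of clinically relevant differences that D.7.b claims. The full-follow-up figure of ±0.64 SD rests only on 40 dyads at 1:1. The 19 and 16 per arm figures, the baseline correlations, the between-outcome correlations and the 0.5 SD benchmark are assumptions. The most favourable case shown, baseline adjustment at r = 0.7 with no attrition, still leaves about ±0.46 SD.

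The clash between the closing section and D.7.c is real on the literal wording but probably unintended; it needs one sentence of alignment.

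**What to change.** 1. **Closing section.** Replace its sentence with: *No hypothesis tests will be done; feasibility rates and between-arm differences are reported with 95% CIs.*
2. **D.7.b.** Replace the sentence on clinically relevant differences with: *Between-arm differences are shown with 95% CIs, adjusted for baseline where collected; point differences alone are not read as clinically relevant.* Align the added-benefits sentence in D.8 with this.
3. **D.7.c.** Say which comparisons the intervals cover, drop the word 'meaningful' for arm comparisons, and state expected half-widths: about ±10 to ±15 points for rates among the 40 enrolled; between arms about ±19 to ±28 points for proportions and ±0.64 SD for unadjusted means, wider with attrition.

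The cost is wording and slightly more analysis work, with no added patients or data. The one drawback for the sponsor is that the stated precision of the arm comparison will look less favourable.
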